12.2 AE COLLECTING AND REPORTING

All AEs spontaneously reported by the patient and/or in response to an open question from study personnel or revealed by observation, physical examination, or other diagnostic procedures will be recorded on the appropriate page of the eCRF starting from the time of ICF signing through the patient's last safety follow-up visit or study discontinuation, whichever is later (ie, the "AE reporting period"). From the time of ICF signing to first dose of mRNA-2146, only AEs related to study procedures will be collected. Also, once a patient has ended study treatment and has initiated any new post-treatment antineoplastic therapy, only AEs suspected to be related to study treatment will be collected.

Any clinically relevant deterioration in laboratory assessments or other clinical findings is considered an AE and must be recorded on the appropriate pages of the eCRF. When possible, signs and symptoms indicating a common underlying pathology should be noted as 1 comprehensive event.

All SAEs that occur during the AE reporting period, as defined by the protocol, must be reported by the investigator to the contract research organization (CRO), as the designee of the Sponsor, within 24 hours of the investigator becoming aware of the SAE. All SAEs and deaths that occur during the AE reporting period, whether or not considered causally related to the study drug, will be reported to the FDA per 21 CFR 312.32. After informed consent, but prior to initiation of study treatment, only SAEs caused by a protocol-mandated intervention will be collected (eg, SAEs related to invasive procedures such as biopsies or medication washout). The information collected will include a minimum of the following: patient number, a narrative description of the event, and an assessment by the investigator as to the intensity of the event and relatedness to study drug. Follow-up information on the SAE may be requested by the Sponsor or its representative CRO. Detailed instructions for the collecting and reporting of SAEs will be provided in the Investigator Site File.

If there are serious, unexpected ADRs associated with the use of the study drug, the Sponsor or its designated CRO will notify the appropriate regulatory agency(ies) and all participating investigators on an expedited basis (7 days for fatal or life-threatening, serious, unexpected ADRs; 15 days for all other serious, unexpected ADRs). The Sponsor has delegated the responsibility to promptly notify the IRB/IEC of all unexpected serious ADRs involving risk to human patients in accordance with the rules and regulations of the IRB/IEC to the PI.

An unexpected event is one that is not reported in the IB.

REPORTING OF SAEs AND SUSPECTED UNEXPECTED SERIOUS ADVERSE REACTIONS

All SAEs must be reported to the designated CRO within 24 hours of the investigational site's knowledge of the occurrence. Each investigational site will submit the SAE information to the CRO.

The SAE information transmitted to the CRO will include the following (as available):

- Patient ID, investigator name, and site number
- SAE information: event term, onset date, severity, and causal relationship
- Basic demographic information (eg, age, sex, weight, etc)
- The outcomes attributable to the event (eg, death, a life-threatening adverse drug experience, inpatient hospitalization or prolongation of existing hospitalization, a persistent or significant disability/incapacity, other important medical event[s])
- A summary of relevant test results, pertinent laboratory data, and any other relevant medical history
- The first and last dates of study drug administration
- A statement whether study drug was discontinued or study drug administration schedule was modified
- A statement whether event recurred after reintroduction of study drug if administration had been discontinued or withheld
- Supplemental information may include the following hospital records: laboratory results, radiology reports, progress notes, admission and emergency room notes, holding or observation notes, discharge summaries, autopsy reports, and death certificates.

The SAE information should be transmitted within 24 hours with as much of the above information as available at the time. Supplemental information may be transmitted and should not delay the initial transmission. The Sponsor or CRO may contact the investigational site to solicit additional information or follow-up on the event. Investigational sites will be provided with detailed instructions on the procedures for transmitting SAEs to the CRO.

For regulatory purposes, initial reports of serious ADRs should be transmitted within the prescribed time frame as long as the following minimum information is available: patient identification, suspect study drug, reporting source, and an event or outcome that can be identified as being both serious and unexpected for which, in the investigator's opinion, there is a suspected causal relationship.

A suspected unexpected serious adverse reaction (SUSAR) that is fatal or life-threatening must be reported to the competent authority and ethics committee immediately (within 7 days) after the Sponsor becomes aware of the event. Any additional information must be reported within 8 days of sending the first report.

A SUSAR that is not fatal or life-threatening must be reported to the competent authority and ethics committee as soon as possible (within 15 days) after the Sponsor becomes aware of the event.

12.3 RELATIONSHIP TO STUDY DRUG

For each reported AE, the investigator must make an assessment of the relationship of the event to each study drug using the following scale:

- Not Related: An event that is not associated with study drug administration and is judged clearly due to causes other than the study drug.
- Related: An event that is or may be associated with study drug administration.

- The terms Possibly Related and Probably Related will not be used. Any event that is possibly or probably related to study drug should be recorded as Related by the Investigator.

In the event of death, the cause of death should be recorded as the AE and the relationship to study drug assessed as above. “Death” is an outcome and is NOT the AE. The only exception is “sudden death” when the cause is unknown.

12.4 LABORATORY TEST ABNORMALITIES

Clinically significant abnormal laboratory findings that are detected during the study or are present at baseline and significantly worsen will be reported as AEs or SAEs. The investigator will exercise his or her medical and scientific judgment in deciding whether an abnormal laboratory finding or other abnormal assessment is clinically significant.

Clinical significance is at the discretion of the investigator and may be defined as those findings which:

- Are directly responsible for discontinuation from the study,
- Require treatment or other therapeutic intervention,
- Require further monitoring, or
- Require further diagnostic evaluation (other than repeat of the same test to confirm the abnormality).

All abnormal laboratory values considered to be clinically significant will be recorded on the AE page of the eCRF. Significant abnormal laboratory values occurring during the clinical study should be followed until repeat tests return to normal, stabilize, or are no longer clinically significant.

12.5 FOLLOW-UP OF AEs

All AEs must be reported in detail on the appropriate page in the eCRF and followed to resolution or stabilization. During the post-treatment follow-up period, all SAEs and related non-serious AEs should be followed until resolution or stabilization, which is defined as grade 1 or less. Patients will be referred to their primary care doctor for further follow-up as needed post-study.

The severity of ongoing AEs at last visit will be recorded. Any additional clinical sequelae emerging from the AE should be recorded as a separate AE.

13 STATISTICAL METHODS

A detailed Statistical Analysis Plan (SAP) will be used to guide the analysis and reporting of data collected in this study.

13.1 DATA COLLECTION AND PROCESSING

Creation and validation of the clinical database, data entry, data management, and transfer of central laboratory data will be conducted in accordance with 21 Code of Federal Regulations (CFR) Part 11 and the Guidance for Industry on Computerized Systems Used in Clinical Trials.

eCRFs will be completed for all enrolled patients. Please refer to the case report form (CRF) Completion Guidelines for instructions on which eCRFs will be completed for patients who are enrolled but not treated.

13.2 SAMPLE SIZE CONSIDERATIONS

No formal sample-size estimation will be performed. The choice of the number of patients will be based on a standard, Phase 1, 3+3 dose escalation design in which 3 to 6 patients are enrolled into each dose cohort.

For the Arm A dose expansion period, the sample size estimation is based on Simon's minimax two-stage design (Richard S, 1989). The null hypothesis that the true overall response rate is 0.05 will be tested, and this design with the sample size of 13 and 14 for the first and second stage, respectively, will provide an overall one-sided alpha value of 0.05 and statistical power of 0.80 when the true overall response rate is 0.20. If there is 1 or more response observed from the 13 subjects in first stage, the study will proceed to the second stage. To account for potential patient drop-out, a total of approximately 30 patients will be enrolled in order to obtain evaluable data from 27 patients. If four or more responses are observed in the 27 evaluable patients, mRNA-2416 will be considered active in ovarian cancer patients, and may warrant further development.

For the Arm B dose expansion period, the sample size estimation is based on Simon's two-stage design (Richard S, 1989). The null hypothesis that the true overall response rate is 0.1 will be tested, and this design with the sample size of 15 and 26 for the first and second stage, respectively, will provide an overall one-sided alpha value of 0.05 and statistical power of 0.80 when the true overall response rate is 0.25. If there is 2 or more responses observed from the 15 patients in first stage, the study will proceed to the second stage. To account for potential patient drop-out, a total of approximately 45 patients will be enrolled in order to obtain evaluable data from 41 patients. If eight or more responses are observed in the 41 evaluable patients, mRNA-2416 in combination with durvalumab will be considered active in ovarian cancer patients, and may warrant further development.

13.3 HANDLING OF MISSING DATA

Details of the handling of missing data will be provided in the SAP.

13.4 STATISTICAL METHODOLOGY

All data collected in this study will be presented in data listings and, where indicated, tabulated in summary tables. Data will be presented and summarized using the SAS System (SAS Institute Inc, Cary, NC).

Continuous variables will be summarized with the number of observations, mean, standard deviation, median, minimum, and maximum.

Categorical variables will be summarized with frequencies and percentages. Percentages will be based on non-missing data unless specified otherwise.

Except where indicated in the SAP, “baseline” is defined as the closest value prior to the start of treatment with study drug.

13.4.1 ANALYSIS POPULATIONS

The following definitions will be used in assigning patients into analysis populations:

- Intent-to-Treat Population – All patients who are enrolled (ie, assigned a patient number).
- Safety Population – All enrolled patients who received any amount of study drug.
- Activity Evaluable Population – All enrolled patient who received any amount of study drug and have at least 1 tumor response evaluation.

13.4.2 SAFETY ANALYSES

All safety analyses will be conducted in the Safety Population.

Verbatim descriptions of AEs will be coded using Medical Dictionary for Regulatory Activities (MedDRA). Summary tables will be provided for all TEAEs. A TEAE is defined as any AE that newly appeared, increased in frequency, or worsened in severity following initiation of study drug. The number and percentage of patients reporting a TEAE in each dose cohort will be tabulated by system organ class and preferred term, severity, and relationship to study drug. The number and percentage of patients reporting a SAE and reporting a TEAE leading to premature discontinuation of study drug in dose cohort will be summarized by system organ class and preferred term. For all analyses of TEAEs, if the same AE (based on preferred term) is reported for the same patient more than once, the AE is counted only once for that preferred term and at the highest severity and strongest relationship to study drug. Clinically relevant abnormal physical examination results are recorded as AEs; thus, physical examination data will not be summarized in a table.

Descriptive statistics for hematology, chemistry, and coagulation data will be summarized by dose cohort and time point and for the overall worst value post-baseline. Toxicity grades will be determined based on the CTCAE criteria version 4.03, and shift tables will be presented. The number and percentage of patients with at least a 2-grade increase from baseline will be summarized by dose cohort.

Descriptive statistics of the change from baseline for vital signs will be summarized by dose cohort and time point. Abnormal values, identified by threshold values defined in the SAP, will be summarized.

Descriptive statistics for ECG parameters at baseline and at the Post-treatment Safety Assessment visit and the change from baseline will be presented by dose cohort.

13.4.3 EFFICACY ANALYSES

The Activity Evaluable Population will be used for the analyses of efficacy data based on the dose of mRNA-2416 received.

Best response will be determined for each patient in accordance with RECIST 1.1, and Cheson guidelines and the objective response rate presented for each dose cohort. The overall objective response rate based on irRC or LYRIC will also be determined. The disease control rate based on RECIST 1.1 will also be

determined for Phase II patients. Progression-free survival and durability of response will be determined using Kaplan-Meier methodology. Please refer to [Appendix C and D](#) for a description of “Immune-related Response Criteria,” and RECIST 1.1 criteria.

The details of Simon’s two-stage study design and analysis used for Arm A and Arm B Phase II will be included in the Statistical Analysis Plan (SAP).

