3.3. Treatment

Two investigational products, mRNA-2416 and durvalumab, are tested on patients with advanced relapsed/refractory solid tumor malignancies or lymphoma. mRNA-2416 is a novel mRNA encoding human OX40L encapsulated in a lipid nanoparticle, administered through repeated intratumoral injections on tumor lesions. Durvalumab in combination with mRNA-2416 in arm B is administered to study patients through intravenous infusion.

Arm A patients receiving treatment to superficial lesions will receive mRNA-2416 on Day 1 and Day 15 of a 28-day cycle for 6 cycles. Arm A patients receiving treatment to visceral lesions and all Arm B patients will receive mRNA-2416 on Day 1 and Day 15 for Cycle 1, and on Day 1 only for Cycles 2-6. All Arm B patients will receive durvalumab in combination with mRNA-2416 on Day 1 in each cycle. Dose levels of mRNA-2416 can be found in the protocol Table 1 and Table 2. In the event that ≥ 2 of the first 6 DLT-evaluable patients in the 8.0 mg cohort experience a DLT, an intermediate dose cohort may be opened at 6.0 mg mRNA-2416. Per protocol, the potential dose cohorts are 0.5 mg, 1.0 mg, 2.0 mg, 4.0

mg, 6.0 mg, and 8.0 mg of mRNA-2416 alone, and 2.0 mg, 4.0 mg, 6.0 mg, and 8.0 mg of mRNA-2416 in combination with durvalumab. Some cohorts may not have any patients enrolled during the course of the study. Only the dose cohorts that have patients enrolled will be analyzed. If the dose level of mRNA-2416 that a patient received at the first dose is different from the dose cohort that the patient was enrolled in, the patient may be analyzed in the dose level of mRNA-2416 that the patient received as specified in the analysis.

Following are the potential treatment arms and dose cohorts for Phase I and Phase II.

- Arm A
 - mRNA-2416 0.5 mg
 - mRNA-2416 1.0 mg
 - mRNA-2416 2.0 mg
 - mRNA-2416 4.0 mg
 - mRNA-2416 6.0 mg
 - mRNA-2416 8.0 mg
- Arm B
 - mRNA-2416 2.0 mg + Durvalumab
 - mRNA-2416 4.0 mg + Durvalumab
 - mRNA-2416 6.0 mg + Durvalumab
 - mRNA-2416 8.0 mg + Durvalumab

4. General Statistical Considerations

This document will provide details regarding the definition of analysis variables and analysis methodology to address all study objectives.

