4.3. Analysis Set

4.3.1. Intent-to-Treat Set

The intent-to-treat (ITT) set will consist of all patients who are enrolled (i.e. signed informed consent form). Patients will be included in the dose cohort to which they were enrolled.

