4.3.2. Safety Set

The safety set will consist of all enrolled patients who received any amount of study drug. Patients will be included in the dose cohort corresponding to the dose level which they actually received.

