4.3.3. Activity Evaluable Set

The activity evaluable set will consist of all enrolled patients who received any amount of study drug and have at least 1 tumor response evaluation. Patients will be included in the dose cohort to which they were enrolled.

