7.3.4. Treatment Modifications

Number of patients with mRNA-2416 injection administered, number of patients without mRNA-2416 injection administered, reason for mRNA-2416 injection not administered, number of patients who had dose modified, categories of dose modification, reason for dose modified, number of lesion injected, and

lesion type will be summarized by scheduled visits, treatment arm and dose cohort for Phase I and Phase II, and total for each treatment arm combining Phase I and Phase II.

Number of patients with durvalumab administered, number of patients without durvalumab administered, action taken with durvalumab, and reason for action on durvalumab will be summarized by scheduled visits and dose cohort for Phase I and Phase II, and total for Arm B combining Phase I and Phase II.

8. Efficacy Analysis

All tables and figures for efficacy evaluations will be conducted using the activity evaluable set by treatment arm and dose cohort (as specified in Section 3.3) for Phase I and Phase II, and total for each treatment arm combining Phase I and Phase II. Listings will be based on the safety set.

Solid tumor response will be assessed by investigators based on RECIST 1.1 (complete response [CR], partial response [PR], stable disease [SD], progressive disease [PD], or not evaluable [NE]), and based on irRC (immune-related complete response [irCR], immune-related partial response [irPR], immune-related stable disease [irSD], immune-related progressive disease [irPD], or not evaluable [NE]). Lymphoma response will also be assessed by investigators based on Cheson 2014 criteria (positron emission tomography [PET]-CT-based complete metabolic response, partial metabolic response, no metabolic response, or progressive metabolic response; CT-based complete radiologic response, partial radiologic response, SD, or PD), and based on LYRIC (PET-CT-based complete metabolic response, partial metabolic response, no metabolic response, progressive metabolic response, or indeterminate response; CT-based complete radiologic response, partial radiologic response, SD, PD, or indeterminate response). Best overall response is determined from time-point overall response. When SD for RECIST 1.1 or irSD for irRC is believed to be the best overall response, it must meet the minimum time (at least 55 days between the first dose date and the last SD assessment date, and no PD between). Death may be considered in determination of best overall response.

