11.6. Statistical Analysis of Pharmacokinetic Parameters

Pharmacokinetic parameters derived from serum concentrations will be individually listed and summarized. The PK parameters with the exception of t_{\max} will display n, mean, standard deviation, CV, geometric mean, median, minimum, and maximum as descriptive statics. However, t_{\max} will only display n, median, minimum and maximum.

For the listings, concentration data will be presented to the same precision as the data is received. All PK parameters will be presented in the listings to 3 significant figures with the exception of t_{\max} , which will be presented to 2 decimal places.

For summary statistics, the following precisions should be used:

- n should be presented to zero decimal places
- CV% should be presented to 1 decimal place
- Mean, standard deviation, geometric mean, median, minimum, and maximum should be presented to the same precision as the listings

12. Interim Analysis

No formal interim analysis is planned.

13. Changes in the Planned Analysis

One of the exploratory endpoints, assessment of the correlation of other investigational serum-based proteins (e.g., anti-drug antibodies) with PK, efficacy, and safety, is not included in this statistical analysis plan.

14. References

Eisenhauer EA et al. New response criteria in solid tumours: revised RECIST guideline (version 1.1). *Eur J of Cancer.* 2009; 45(2):228-247.

DocuSign Envelope ID: B20D66AA-D718-4BD5-9F79-8CFF4FE948CA

Statistical Analysis Plan (SAP) Client Approval Form

Client:	ModernaTX, Inc.
Protocol Number:	mRNA-2416-p101
Document Description:	Final Statistical Analysis Plan
SAP Title:	A Phase I/II, Open-label, Multicenter, Dose Escalation and Efficacy Study of mRNA-2416, a Lipid Nanoparticle Encapsulated mRNA Encoding Human OX40L, for Intratumoral Injection Alone and in Combination with Durvalumab for Patients with Advanced Malignancies
SAP Version Number:	1.0
Effective Date:	29NOV2021
Author(s):	
For PPD: PPD	
For Moderna: PPD	
Approved by:	
PPD	Date (DD-MMM-YYYY)
Biostatistics and programming, PPD	
PPD	Date (DD-MMM-YYYY)
Clinical Development, Moderna, Inc.	
PPD	Date (DD-MMM-YYYY)
Biostatistics, Moderna, Inc.

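### The SAP groups efficacy by enrolled dose cohort although the protocol says dose received, so if a first dose differs from the cohort, Phase I response by dose will not line up with safety, PK or the efficacy listings

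*Protocol*

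**What the plan says.** **Dose grouping.** Protocol Section 13.4.3 sets the rule for efficacy: "The Activity Evaluable Population will be used for the analyses of efficacy data based on the dose of mRNA-2416 received". SAP Section 8 names the set and layout: "All tables and figures for efficacy evaluations will be conducted using the activity evaluable set by treatment arm and dose cohort". SAP Section 4.3.3 then fixes the dose column for that set: "Patients will be included in the dose cohort to which they were enrolled". The safety set in SAP Section 4.3.2 follows the opposite rule: "Patients will be included in the dose cohort corresponding to the dose level which they actually received". The PK set in Section 4.3.4 follows the same rule as the safety set. SAP Section 8 also runs the efficacy listings on the safety set.

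SAP Section 3.3 anticipates a patient whose first mRNA-2416 dose "is different from the dose cohort that the patient was enrolled in". It allows analysis by dose received, but leaves the choice to each individual analysis.

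**ITT.** Protocol Section 13.4.1 has "All patients who are enrolled (ie, assigned a patient number"; SAP Section 4.3.1 has "all patients who are enrolled (i.e. signed informed consent form".

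**Record of changes.** SAP Section 1 says the SAP prevails where the two documents differ. SAP Section 13 lists one change only: "One of the exploratory endpoints, assessment of the correlation of other investigational serum-based proteins" is dropped. Neither difference above appears there.

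**The concern.** A dose-escalation report is read across: response, toxicity and exposure for the same patients at the same dose. Under the SAP, a patient given a dose other than the cohort's would have adverse events and concentrations in one dose column and tumor response in another. The efficacy table and the efficacy listing could also show that patient at different doses. Both documents further plan to relate outcomes to the dose of mRNA administered (protocol Section 7.6, SAP Section 3.2.3), which means dose received.

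The usual reason for analysing patients as assigned is to protect a randomised comparison. There is no randomisation here, so in Phase I nothing is gained by filing a response under a dose the patient did not get. What is at stake is a coherent Phase I response-by-dose display and a record of why the protocol rule was dropped.

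**Working it through.** The plan gives no figure on this point, so the main check compares the texts. The arithmetic that follows is an illustration.

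**1. Which dose column applies**

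| Output | Set | Dose column |
|---|---|---|
| Efficacy, protocol 13.4.3 | Activity evaluable | Dose received |
| Efficacy tables and figures, SAP 8 with 4.3.3 | Activity evaluable | Cohort enrolled |
| Efficacy listings, SAP 8 with 4.3.2 | Safety | Dose received |
| Safety, SAP 9 with 4.3.2 | Safety | Dose received |
| PK, SAP 11.1 with 4.3.4 | PK | Dose received |

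The second row is the only one that differs. SAP Section 3.3 does not resolve it: it defers to the specific analysis, and Section 4.3.3 specifies enrolled cohort.

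**2. Size if one mismatch occurs**

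Inputs: cohorts of 3 to 6 (protocol Section 13.2). Assumption: one patient enrolled in a cohort of size n received another dose level.

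If that patient is the cohort's only responder, ORR in the enrolled cohort is 1/n by enrolled dose and 0/(n − 1) by dose received:
- n = 3: 1/3 against 0/2, a difference of 33 points.
- n = 6: 1/6 against 0/5, a difference of 17 points.

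In a receiving cohort of size n with no responder of its own, ORR is 0/n by enrolled dose and 1/(n + 1) by dose received:
- n = 3: 0/3 against 1/4, a difference of 25 points.
- n = 6: 0/6 against 1/7, a difference of 14 points.

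If a 3+3 cohort of 6 takes its full 9 biopsy-enrichment patients, n = 15. The enrolled cohort then changes by 1/15 = 7 points.

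**3. Phase II decision rule**

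The Simon designs in protocol Section 13.2 count responses per arm. Their operating characteristics follow from the sum over stage-1 responses x ≥ r1 of P(X1 = x) × P(X2 ≥ r − x), where r1 is the number needed to continue and r the number needed to be called active:
- Arm A (13 then 27 patients; continue at 1, active at 4): alpha 0.0416 at a true ORR of 0.05, power 0.801 at 0.20.
- Arm B (15 then 41 patients; continue at 2, active at 8): alpha 0.0430 at 0.10, power 0.803 at 0.25.

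Both agree with the stated 0.05 and 0.80. Dose grouping does not alter them, provided every evaluable patient stays in the arm's count.

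**4. ITT**

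Consent comes before any study procedure (protocol Section 16.1). Both documents put screening before enrollment (protocol Section 8.3, SAP Section 3.1), and protocol Section 15.2 has investigators enroll only patients who met the eligibility criteria. Read literally, SAP Section 4.3.1 therefore admits screen failures. It also files every ITT patient under an enrolled dose cohort, which a screen failure would not have.

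The ITT set feeds only the analysis-set summary and one listing (SAP Section 5.1). Disposition uses the safety set (SAP Section 5).

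**The case against.** **The effect may be nil.** Protocol Section 10.1 requires tumor large enough for the first planned dose. Section 8.2.2 lets enrichment patients with too little injectable volume join a lower level. Later reductions do not matter, because SAP Section 3.3 looks at the first dose. Treatment data are listed, so a mismatch could be seen. Arm totals, waterfall plots by arm and the PFS curves pooled over dose do not change. All of this stands. So does the remark that 1/3 has an exact 95% interval of about 1% to 91%, so no inference turns on one such cohort.

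**A reader might infer that the grouping distorts RDE selection.** The documents do not support that. Protocol Section 8.4.1 has the safety review committee assess safety data and treatment status during the trial. Section 8.4.3 bases the MTD on DLTs and feeds later DLT-type events into the RDE, and Section 8.2.1 adds adverse events in the enrichment cohorts. Response and PK are not named as inputs. The SAP, dated 29 November 2021, governs final tables and not those meetings.

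**A reader might infer that the SAP certainly widens ITT, or that drop-out figures are distorted.** The first is likely but unproven. The protocol does not say when a patient number is assigned, and Section 12.2, in a paragraph that covers pre-treatment events, expects SAE information to carry one. If numbers are given at consent, the two definitions coincide. The second fails, because disposition uses the safety set.

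**The SAP states its rules openly and prevails.** True, but that settles which text governs. It neither explains the change nor removes the conflict among the SAP's own sets.

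**Conclusion.** The inconsistency is real and rests on plain text: protocol Section 13.4.3 and SAP Section 4.3.3 give opposite dose-grouping rules for efficacy, the SAP's safety, PK and efficacy-listing rules side with the protocol, and SAP Section 13 is silent. The consequence is conditional. It needs at least one patient whose first dose differed from the enrolled cohort, and the documents give no count. Given one, and given that this patient is the sole responder, the enrolled cohort's ORR changes by 33 or 17 points (n = 3 or 6), and a responder-free receiving cohort of the same size by 25 or 14 points. The matter is confined to Phase I response by dose and its agreement with the other displays. RDE selection is unaffected, as is the Phase II decision if the arm counts are kept whole.

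The ITT wording is a minor companion point. SAP Section 4.3.1 sits badly with SAP Section 3.1 and with its own cohort instruction, but no efficacy, safety or drop-out estimate depends on it.

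**What to change.** - **SAP Section 4.3.3:** assign Phase I patients to the dose cohort of the first mRNA-2416 dose received, in line with protocol Section 13.4.3 and the safety and PK sets. State that every evaluable Phase II patient remains in the arm's two-stage count, whatever first dose was given.
- **SAP Section 4.3.1:** return to the protocol's definition by assigned patient number, add that enrollment follows confirmed eligibility (a clarification, since the protocol definition does not say so), and report screen failures on a separate line.
- **SAP Section 13:** list any remaining difference from the protocol, with the reason.

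The cost is a few sentences in the SAP and a grouping variable in the efficacy programs. No new data are needed. If no patient's first dose differed from the enrolled cohort, the dose-grouping change alters no number, and a sentence saying so would close that part of the point.
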